1 INTRODUCTION

Approximately 22% of new contact lens (CL) wearers cease contact lens wear within the first year, with handling (25%), poor distance (23%) and/or near vision (21%) and discomfort (21%) being the main reasons for discontinuation.¹ With today's ever-expanding access to digital devices, the number of potential CL wear drop-outs may further be affected by digital device use. A recent review found a higher prevalence of symptoms of eye strain, eye fatigue or blurred vision in CL wearers compared to non-CL wearers (65% vs 50%) when using digital devices.² The symptoms associated with digital device use in contact lens wear may be affected by multiple factors, including an insufficient blink rate or a poorly wetting contact lens.

Time to haze (TTH) is a metric that has been developed at CORE to measure the maximum time a contact lens wearer can keep their eye open without their vision becoming hazy (conducted just above contrast threshold level); it is a measure of how the drying of the CL surface with open eyes affects vision.

Alcon has recently introduced a new silicone hydrogel (SiHy) daily disposable contact lens (DD CL), called Precision1, which is manufactured from the verofilcon A material. Precision1 DD CLs use 'SMARTSURFACE Technology; which Alcon describe as "*a permanent, micro-thin, high-performance layer of moisture at the lens surface that helps support a stable tear film to deliver lasting visual performance from morning to night*".³

The purpose of this study is to evaluate the performance of Precision1 DD CLs with regard to subjective symptoms (dryness, comfort, vision), lens fit and time to haze in CL wearers who identify themselves as heavy digital devices users (at least 6 hours of digital device use per day).

2 OBJECTIVES

The objectives of the study are:

- To assess subjective ratings for contact lens comfort, dryness and clarity of vision after insertion, after 6hrs of digital devices use and at the end of day in heavy digital devices users while wearing Precision1 for two weeks.
- To determine subjective satisfaction with Precision1 CLs when using digital devices.

The primary outcome variables for this study are:

- Subjective ratings of CL comfort, dryness, clarity of vision after insertion, after 6hrs or more using digital devices, and at the end of day (0 to 100 scale).

Other outcome variables of interest include

- Likert type questions exploring the satisfaction with Precision1 CLs when using digital devices.
- Lens fit
- Lens surface characteristics (wettability, pre-lens tear break-up time & deposits)
- Time to haze
- Conjunctival redness
- Visual acuity

3 HYPOTHESIS

Precision1 CLs will provide a satisfactory performance for heavy digital device users as reflected in subjective ratings for comfort, dryness and clarity of vision.

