4.2 STUDY POPULATION

4.2.1 SAMPLE SIZE CALCULATION

The sample size required for a 2-tailed matched paired t-test to detect a change of 5 points in a 0-100 subjective rating scale, with $\alpha=0.05$, power = 0.90, and an effect size of 0.60 is 32 to complete the study, i.e. a minimum sample size of 32 participants completing the study.

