4.4 SCHEDULED AND UNSCHEDULED VISITS

There will be three study visits, including a screening visit. Participants will attend the clinical site for a total of 2.5 hours. Participants will also be asked to complete at home ratings on Day 1, Day 7 and Day 10, to assess their experience with the study CL.

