4.4.3 BASELINE & DISPENSE (VISIT 2)

Participants who successfully met all eligibility criteria will directly transition to Visit 2, while continuing to wear the pair of study lenses that has just been fitted.

1. Subjective post-insertion ratings (0-100 scale, where 100 means better performance; integer steps, both eyes rated together), to assess the first impression of Precision1 regarding:
 - *Comfort;*
 - *Dryness;*
 - *Clarity of vision;*
2. Lens fit & surface assessment
3. Time to haze
4. Lens dispense: Participants will be provided with a supply of Precision1 CLs to last them until their next study visit (12-16 days after V2).
5. At-home rating scales: Participants will receive at home rating scales, to be completed on Day 1, Day 7 and Day 10.
6. Participant instructions. The participants will be asked to:
 - *Wear the lenses at least 5 days per week and 10 hours per day throughout the study;*
 - *To complete subjective ratings at home to reflect their lens wear experience on Day 1 (the day after V2), Day 7 and Day 10 using a 0-100 scale, where 100 means better performance; integer steps, both eyes rated together). Ratings will be completed at lens insertion, after 6 hours of digital device use, and just before CL removal. Variables to be assessed are:*
 - *Comfort*
 - *Dryness*
 - *Clarity of vision*
 - *Attend V3 after 6 hours or more of Precision1 study lens wear;*

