4.4.4 DAY 14 FOLLOW-UP & EXIT (VISIT 3)

Participant to attend visit after 6 hours or more of Precision1 study lens wear.

1. Collect unused study CLs;
2. Changes in medical history/medications;
3. Compliance with # of CL wear days/hours per day (total & comfortable) and # hours of digital device use over past 2 weeks and for V3 visit day;
4. Collect and review at-home ratings;
5. Study CL logMAR HIHC VA for OD, OS and OU;
6. Subjective ratings (0-100 scale, where 100 means better performance; integer steps, both eyes rated together), to assess a typical day in the past 2 weeks for insertion, after 6 hours of digital device use, and just before CL removal.
 - *Comfort*
 - *Dryness*
 - *Clarity of vision*
7. Satisfaction (4-point Likert scale: strongly disagree, slightly disagree, slightly agree, strongly agree) with Precision1 CLs overall and when using digital devices on a typical day in the past 2 weeks
8. Lens fit & surface assessment
9. Time to haze
10. Lens removal
11. Biomicroscopy examination

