4.5.2 SUBJECTIVE RATINGS

Subjective ratings:

At visit 2, participants will be provided with subjective rating 0-100 questionnaires to assess their first impression with the study CLs post insertion regarding comfort, dryness and clarity of vision.

At the end of visit 2, they will be provided with at-home questionnaires to subjectively rate the experience with the study lenses regarding comfort, dryness and clarity of vision using a 0-100 scale (integer steps; both eyes together), where 100 means better performance. This questionnaire will be completed at home on Days 1, 7 and 10 after Visit 2 (i.e. Day 0), at three different time-points on each of these days: directly after insertion, after 6 hours of digital device use, and at the end of day just before lens removal. In addition, times of lens insertion, first notice of discomfort, and lens removal will be collected.

The same questionnaire will be provided to the participants during V3 to assess their overall 'typical day' experience during the past 2 weeks.

Satisfaction with study CL:

Satisfaction (4-point Likert scale: strongly disagree, slightly disagree, slightly agree, strongly agree) with Precision1 CLs overall and while using digital devices on a typical day in the past 2 weeks will be assessed for the following questions:

- *The study lenses provide good vision all day long;*
- *The study lenses provide good comfort all day long;*
- *I am satisfied with the comfort the study lenses provide when I use digital devices for ≥ 6 hours;*
- *I am satisfied with the vision the study lenses provide when I use digital devices for ≥ 6 hours;*
- *I don't experience eye strain when I wear the study lenses and use digital devices for ≥ 6 hours.*
- *I don't experience eye fatigue (tired eyes) when I wear the study lenses and use digital devices for ≥ 6 hours.*
- *I don't experience episodes of blurred vision when I wear the study lenses and use digital devices for ≥ 6 hours.*

- Overall, these lenses provide good performance when using digital devices for ≥ 6 hours.

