10 STATISTICAL ANALYSIS AND DATA MANAGEMENT

10.1 STATISTICAL ANALYSIS

All data will be analyzed by CORE at the University of Waterloo. Data analysis will be conducted using Statistica, SPSS, or other appropriate software.

Descriptive statistics will be provided for all primary outcome variables as well as information regarding baseline variables (e.g. age, sex).

Subjective ratings, lens fit assessments and time to haze will be compared between Visit 2 (Precision1 Dispense) and Visit 3 (2-week follow-up) using either Paired t-tests or Wilcoxon matched pairs, or using ANOVA, as applicable; statistical significance will be set at 5%. The appropriate tests will be selected based on tests of normality - non-parametric tests will be used for data not showing a normal distribution. For assessments conducted for each eye separately, the right eye will be used for analysis if there is no difference between eyes.

Binomial testing will be conducted to analyze Likert questionnaires (strongly agree, slightly agree, slightly disagree, strongly disagree) to determine whether participants had a positive or negative experience with the test lens.

Additional analysis may be conducted.

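### Section 3 hypothesises a satisfactory level on the ratings, but the only comparison 10.1 names for them is change from Visit 2 to Visit 3, which cannot test a level and has a Visit 2 value for only three of the nine primary ratings

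*Combined protocol and SAP*

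**What the plan says.** The hypothesis in Section 3 is that "Precision1 CLs will provide a satisfactory performance for heavy digital device users as reflected in subjective ratings for comfort, dryness and clarity of vision". Section 2 makes the primary outcomes comfort, dryness and clarity of vision, each rated 0-100 at three times of day: after insertion, after 6 hours or more of device use, and at end of day. That is nine ratings.

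Section 10.1 has one sentence that names a comparison for them: "Subjective ratings, lens fit assessments and time to haze will be compared between Visit 2 (Precision1 Dispense) and Visit 3 (2-week follow-up"), by paired t-test, Wilcoxon matched pairs or ANOVA, at the 5% level. Section 4.2.1 sizes the study "to detect a change of 5 points in a 0-100 subjective rating scale" with a two-tailed paired t-test. It does not say between which visits; Visit 2 to Visit 3 is the natural reading in the light of 10.1.

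The ratings come from three places:
- Visit 2 (Section 4.4.3): post-insertion only, "to assess the first impression of Precision1 regarding" the three variables.
- Home (Section 4.5.2): "This questionnaire will be completed at home on Days 1, 7 and 10 after Visit 2", at all three times of day.
- Visit 3 (Section 4.4.4): "to assess a typical day in the past 2 weeks for insertion, after 6 hours of digital device use, and just before CL removal".

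Two other parts of 10.1 bear on level. First, "Descriptive statistics will be provided for all primary outcome variables". Second, a binomial test of the Likert items is to show whether the experience with the lens was positive or negative. Section 2 lists those items among the other outcomes, not the primary ones.

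**The concern.** Satisfactory is a statement about level, and a test of change does not look at level. Ratings could be poor at both visits and improve significantly, or be excellent at both and show no change. If the Visit 2 to Visit 3 p-value is read as the test of Section 3, the conclusion will not follow from the analysis.

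The comparison also does not reach the ratings that motivate the study. Its interest is in heavy device users after hours of screen work, and those ratings have no Visit 2 value to be compared with. They exist in two forms, same-day home ratings and a two-week recall at Visit 3, and 10.1 does not say which is the main one. That leaves the headline source open until after the data are in hand.

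**Working it through.** **1. The plan's own figure.** Inputs from Section 4.2.1: two-tailed paired t-test, alpha 0.05, power 0.90, effect size 0.60, change of 5 points. Exact noncentral-t power is 0.898 at n = 31 and 0.908 at n = 32, so the stated 32 completers is correct. The implied SD of differences is 5 / 0.60 = 8.33.

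**2. What the paired test responds to.** The statistic is t = mean change / (SD of differences / √n). The level does not appear in it. The standard error is 8.33 / √32 = 1.473.

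| Visit 2 mean | Change | t | p |
|---|---|---|---|
| 40 | +5 | 3.39 | 0.0019 |
| 85 | +5 | 3.39 | 0.0019 |
| 85 | -5 | -3.39 | 0.0019 |
| 40 | 0 | 0 | 1.0 |
| 90 | 0 | 0 | 1.0 |

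The means of 40, 85 and 90 are illustrations. The smallest mean change that reaches significance is t(0.975, 31) × 1.473 = 2.0395 × 1.473 = 3.00 points, at any level. Neither a significant nor a non-significant result says whether the ratings are satisfactory.

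**3. Which primary ratings the comparison can use.**

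| Time of day | Ratings | Visit 2 | Home, Days 1, 7, 10 | Visit 3 |
|---|---|---|---|---|
| After insertion | 3 | yes, immediate | yes, same day | yes, recalled |
| After 6 hours of device use | 3 | none | yes, same day | yes, recalled |
| End of day | 3 | none | yes, same day | yes, recalled |

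A like-for-like time point exists for 3 of 9 ratings; 9 - 3 = 6 have no Visit 2 value. Even the three pairs set an immediate first impression against a recalled typical day, so a difference mixes any real change with the change in what is asked.

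**4. What 32 completers give for a level.** The documents state no SD for rating levels, so these are assumptions. With one rating per participant, the 95% confidence interval half-width is 2.0395 × SD / √32:
- SD 10: 3.6 points
- SD 15: 5.4 points
- SD 20: 7.2 points

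If a benchmark were set, the true distance above it detectable with 90% power (two-sided 5%, n = 32) is 0.5916 × SD: 5.9, 8.9 and 11.8 points for the same SDs.

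**The case against.** The strongest reply is that this is an open-label pilot whose objectives are to assess ratings and determine satisfaction. Neither promises a confirmatory test. Descriptive statistics serve the first objective and the Likert binomial test the second, so little depends on a loosely worded hypothesis.

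Much of that stands, and it rules out several stronger readings:
- *The device-use and end-of-day ratings go unanalysed.* Not so. Descriptive statistics are promised for all primary outcomes, and Section 2 includes these ratings among them. What is missing is an inferential analysis or criterion.
- *Nothing in the plan tests satisfaction.* Also not so. The Likert items have a built-in agree/disagree split and cover comfort and vision with at least 6 hours of device use. They do not close the gap, because they are not primary, none of the eight asks about dryness (which Section 3 names), and the hypothesis points to the comfort, dryness and vision ratings. The unstated null proportion is missing detail, not part of this point.
- *Most of the rating data are lost.* The 27 home entries per participant (3 days × 3 times × 3 variables) have no named comparison, but they repeat the same nine variables that Visit 3 also collects. The fair count is six of nine ratings without a Visit 2 value.
- *The sample size is wrong.* It is correct for a paired change.

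One could add that 10.1 allows ANOVA and further analysis. The sentence naming ANOVA is confined to Visit 2 versus Visit 3, and permission for additional analysis specifies nothing. The pilot label lowers the weight of the point, but the protocol still states a hypothesis, 90% power and a 5% significance level, and these should refer to the same question.

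**Conclusion.** The point holds as a mismatch between hypothesis and named test, and should be fixed. Followed as written, the Visit 2 to Visit 3 comparison cannot support or refute Section 3, and it has a like-for-like time point for three of the nine primary ratings. This rests on reading the hypothesis as a claim about level, and on the absence of any criterion for the 0-100 ratings in the documents. The non-dependence on level is algebra and needs no assumption; only the precision figures rest on assumed SDs of 10 to 20.

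A reader might infer that the sponsor intends to choose between home and Visit 3 ratings after seeing them. The documents do not show that; they only leave the choice open.

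**What to change.** In Section 10.1:
- Make the main analysis of the nine primary ratings their estimated level: mean or median with a 95% confidence interval.
- Name one source before enrolment, either the Visit 3 typical-day ratings or the Day 1, 7 and 10 home ratings, and report the other as supportive. Home ratings avoid two-week recall but depend on home completion; Visit 3 ratings are collected on site but are recalled. If home ratings are chosen, say which day is used or that the three are averaged.
- Limit the Visit 2 to Visit 3 comparison to the three post-insertion ratings, as secondary, labelled as first impression versus recalled typical day.

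In Section 3, reword the hypothesis as descriptive estimation, or state a benchmark justified before enrolment. In either case, do not conclude that performance is satisfactory from the change test.

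The cost is wording only: no extra participants, visits or data. The downside is that, without a benchmark, the conclusion becomes descriptive, and that the sponsor commits to one rating source in advance.

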4 MATERIALS AND METHODS

4.1 STUDY DESIGN

4.1.1 OVERALL DESIGN

This is a prospective, non-masked, open-label, dispensing pilot study with three study visits on two study days. CL wearers who identify themselves as using digital devices for at least 6 hours on a typical day will be enrolled. Eligible participants will be dispensed with the Precision1 study lenses for a duration of 14 ± 2 days, to be worn for at least 5 days a week and at least 10 hours per day:

- **Visit 1:** Screening and fitting of study lens (1.0 hour)
- **Visit 2:** Baseline & Dispense (0.5 hours; same day as and directly after V1)
- **Visit 3:** Day 14 Follow-up and study exit (1.0 hour)

4.1.2 MASKING

This is an open-label study that will not involve masking.

4.2 STUDY POPULATION

4.2.1 SAMPLE SIZE CALCULATION

The sample size required for a 2-tailed matched paired t-test to detect a change of 5 points in a 0-100 subjective rating scale, with $\alpha=0.05$, power = 0.90, and an effect size of 0.60 is 32 to complete the study, i.e. a minimum sample size of 32 participants completing the study.

4.2.2 NUMBER OF PARTICIPANTS

Participants will be recruited / screened using CORE records and advertising approved by the UW Office of Research Ethics. Up to 35 participants who meet all eligibility criteria may be dispensed with Precision1 study lenses and asked to wear these lenses for 14 ± 2 days, with a target of 32 completing the study. Participants who were screened but did not meet all eligibility criteria are not included in the number of participants (n=35) to be dispensed. Informed consent will be obtained for all participants prior to their enrolment in the study (Appendix 1).

4.2.3 INCLUSION AND EXCLUSION CRITERIA

A person is eligible for inclusion in the study if he/she:

1. Is between 18 and 40 years of age (inclusive) and has full legal capacity to volunteer;
2. Has read and signed an information consent letter;
3. Is willing and able to follow instructions and maintain the appointment schedule;
4. Is a heavy digital device user (at least 6 hours on a typical day using any combination of digital devices such as PC, laptop, smartphone, or tablet);
5. Is a habitual wearer of daily, spherical, soft contact lenses (no bifocal or multifocal contact lenses, no extended wear or monovision, not a current wearer of Precision1 lenses) for at least 5 days/week and at least 10 hours/day during the month prior to enrollment;
6. Has a vertex corrected spherical equivalent distance refraction that ranges between -0.50D to -6.00D in each eye;
7. Has a vertex corrected refractive cylinder of no more than -1.00D cylindrical correction in each eye after vertexing to the corneal plane;
8. Demonstrates an acceptable fit and achieves best corrected visual acuity of at least 0.20 log MAR in each eye with Precision1 contact lenses;

9. Is willing to wear Precision1 CLs at least 5 days per week and 10 hours per day throughout the study;

A person will be excluded from the study if he/she:

1. Is participating in any concurrent clinical or research study;
2. Has any known active* ocular disease and/or infection;
3. Has a systemic condition that in the opinion of the investigator may affect a study outcome variable;
4. Is using any systemic or topical medications that in the opinion of the investigator may affect a study outcome variable;
5. Has known sensitivity to the diagnostic pharmaceuticals to be used in the study;
6. Is pregnant, lactating or planning a pregnancy at the time of enrolment;
7. Is aphakic;
8. Has undergone refractive error surgery;

* For the purposes of this study, active ocular disease is defined as infection or inflammation which requires therapeutic treatment. Mild (i.e. not considered clinically relevant) lid abnormalities (blepharitis, meibomian gland dysfunction, papillae), corneal and conjunctival staining and dry eye are not considered active ocular disease. Neovascularization and corneal scars are the result of previous hypoxia, infection or inflammation and are therefore not active.

Age >40 years is excluded because presbyopia and pre-presbyopia is highly prevalent in this population and will cause eyestrain which is unlikely to be improved with a change in contact lens material.

Pregnant and lactating women are not being excluded from the study due to safety concerns but due to fluctuations in refractive error and/ or visual acuity that occur secondary to systemic hormonal changes. It has further been shown that pregnancy could impact tear production, which could impact dry eye symptoms. Such fluctuations could affect data, thereby negatively affecting study data integrity.

4.2.4 REPEATED SCREENINGS

In some circumstances a repeated screening may need to be scheduled (Visit 1-R). Examples include, but are not limited to:

1. Incomplete information available at time of screening to determine eligibility (e.g. current lens brands worn, history from current eye care practitioner etc.)
2. Study procedures unable to be completed in time scheduled for visit;
3. Study products not available at the time of the screening visit;
4. A transient health condition which may affect the eye(s) (e.g. a common cold, active allergies, fatigue etc.);
5. The short term use of medications (e.g. antibiotics, antihistamines etc.)
6. Reassessment of baseline ocular conditions (e.g. corneal and/or conjunctival staining, scars etc.)

The maximum total number of screenings permitted will be 2, i.e. 1 re-screen is permitted.

4.3 STUDY MATERIALS

4.3.1 LENSES

All study lenses are approved by Health Canada. They will be worn bilaterally, and on a daily disposable basis, therefore no lens care solution is required.

Table 1: lens characteristics

Lens	Precision1
Material	verofilcon a
HC licence #	101910
Medical device class	2
Dk/t (barrer/cm)	100
Water content	51%
Sphere power (D)	-0.50 to -6.00 (0.25 steps)
Base curve (mm)	8.3
Diameter	14.2
Replacement schedule	Daily disposable

4.3.2 REWETTING DROPS

Participants will not be encouraged to use rewetting drops; however, those who habitually used rewetting drops will be allowed to continue using their normal drops. Rewetting drop use will be recorded at each visit.

4.3.3 ORDERING CONSUMABLES

Precision1 study lenses will be supplied by Alcon for the use in this study.

